### *Exclusion criteria*

1. History of acute cardiac ischemia
2. History of hypersensitivity reaction to Lumason
3. Pregnancy

## **Methods**

Potential subjects will be identified by three methods.

- 1) From the MRI schedule at the performance site, a radiology investigator will prospectively identify patients who are to undergo abdominal MRI with hepatobiliary contrast and who otherwise meet entry criteria. Exclusion criteria will be evaluated by consulting the medical record. At the time of MRI scanning, a radiology investigator will meet with the potential subject, confirm that exclusion criteria are not met, explain the study, answer any questions, and seek written informed consent. If consent is granted, CEUS of the liver will be scheduled.
- 2) From the surgery/hepatology clinic schedule, a surgery or hepatology investigator will identify patients who meet entry criteria. The investigator will explain the study to the patient; if he/she expresses interest, the investigator will give a copy of the informed consent to the potential subject, and contact radiology and have the patient scheduled for CEUS of the liver. At the time of CEUS, a radiology investigator will meet with the potential subject, confirm that exclusion criteria are not met, explain the study, answer any questions, and seek written informed consent.
- 3) The principle investigator will retroactively review the radiology database, DORIS, for patients who have had a recent MRI with hepatobiliary contrast and who otherwise meet entry criteria that may have been missed by the previous methods mentioned. A study

radiology investigator will reach out to the patient's hepatologist about enrolling them in the trial and obtain best contact information. A study coordinator will contact the patient by email or phone, with IRB approved script, to seek consent to contact for recruitment purposes.

The subjects will be scanned in the University or Methodist Hospital ultrasound department by technicians trained in use of CEUS, under supervision of one of the study's key personnel. The contrast agent used will be Lumason (sulfur hexafluoride lipid-type A microspheres) distributed by Bracco Diagnostics Inc. Previous MRI images will be reviewed, and up to two of the largest lesions will be evaluated. Each lesion will be interrogated with a single intravenous dose of contrast (2.5 mL). If there is a single lesion, a second 2.5 mL injection may be used as needed to improve lesion visualization. If there are two lesions, each will be evaluated with one injection. Since the intention to treat includes all lesions chosen from MRI, if the injection(s) do not provide adequate images, the lesion in question will not be excluded from the study.

Once the study is closed to enrollment and all subjects have completed the research CEUS scan. The obtained CEUS images will then be reviewed in consensus by two radiologist investigators, blinded to clinical information and MRI findings. Each lesion assessed will be given a presumed diagnosis of FNH, HA, or indeterminate. At the completion of the study, the CEUS data will be compared to the official reports from the MRIs dictated by IUH radiologists to assess concurrence between the two imaging modalities.

The PI and another investigator will quarterly review data quality, subject recruitment, accrual, outcome and adverse event data; assess scientific reports or therapeutic development, results of related studies that may impact subject safety, and procedures designed to protect the privacy of subjects.

We will compile descriptive statistics comparing the sensitivity, specificity, and accuracy of CEUS for differentiating FNH and hepatic adenoma, compared with MRI results as the gold standard.

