## **Enrollment**

As this study explores a new method of diagnosing hepatic lesions and there is little published data on the subject, we do not have sufficient knowledge to do power and sample size calculations to demonstrate the number of patients needed to show equivalence between the two imaging methods. The proposed enrollment of 40 patients reflects the availability of both Lumason and the approximate number of qualifying patients who would undergo MRI for evaluation of these lesions in one year.

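### Does allowing a repeat injection only for single-lesion patients make the CEUS accuracy figures an ill-defined mixture?

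*Protocol*

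**What the plan says.** All the relevant rules are in the protocol's Methods section. For each patient, "up to two of the largest lesions will be evaluated". The default is one 2.5 mL injection per lesion. The exception follows directly: "If there is a single lesion, a second 2.5 mL injection may be used as needed to improve lesion visualization". For the other case, "If there are two lesions, each will be evaluated with one injection".

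Poor images do not remove a lesion: "if the injection(s) do not provide adequate images, the lesion in question will not be excluded from the study". After enrollment has closed and all scans are done, two blinded radiologists read the images in consensus, and "Each lesion assessed will be given a presumed diagnosis of FNH, HA, or indeterminate". The stated analysis is descriptive: "We will compile descriptive statistics comparing the sensitivity, specificity, and accuracy of CEUS for differentiating FNH and hepatic adenoma", with MRI as the gold standard.

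The Enrollment section sets 40 patients by availability and makes no power or sample size calculation. With one or two lesions per patient, that gives 40 to 80 lesions.

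**The concern.** Read together, these rules seem to apply two versions of the index test. A lesion that is alone can have a second chance at adequate images; a lesion that is one of two cannot. Because inadequate lesions stay in and each lesion has one label, any overall accuracy averages over both conditions, and the weights depend on how many two-lesion patients happen to enroll.

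If repeats rescue some poor images, the figure could move with case mix although CEUS performs the same per injection. A later study planned from this pilot might then not know which imaging condition the figure describes. If the readers see all images before giving their one diagnosis, what they would have said after the first injection alone is lost.

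**Working it through.** **Reading the rules together.** The one-injection default and the optional second injection are a general rule followed by an exception, not a contradiction. One lesion means one injection, or two if needed; two lesions mean one each. Both cases come to at most two injections per patient. An as-needed repeat can be part of an imaging test as performed. The accuracy of CEUS under this rule is therefore a defined quantity, and the plan as written estimates it.

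**Is there a stated figure to check?** No. The protocol gives no expected accuracy, no rate of inadequate images and no rate of repeats. What follows is an illustration on assumed values.

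**Inputs.** From the protocol: 40 patients, one or two lesions each. Assumed: 90% correct when images are adequate; a share f of first injections inadequate; every such single lesion repeated; the repeat also inadequate in a share c of those; inadequate images counted as not correct; k patients with two lesions.

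**Formulas.**
- Single-lesion accuracy = 0.9 × (1 − f × c)
- Two-lesion accuracy = 0.9 × (1 − f)
- Gap = 0.9 × f × (1 − c)
- Overall accuracy = [(40 − k) × single + 2k × two-lesion] / (40 + k)
- 95% half-width = 1.96 × √[p(1 − p) / (40 + k)], lesions treated as independent

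**Gap between the groups.** At f = 0.2, two-lesion accuracy is 0.9 × 0.8 = 72.0%. Single-lesion accuracy is 86.4%, 81.0%, 75.6% and 72.0% for c = 0.2, 0.5, 0.8 and 1.0, so the gap is 14.4, 9.0, 3.6 and 0 points. At c = 0.5 it is 4.5 points for f = 0.1 and 13.5 for f = 0.3.

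**Movement with case mix** (f = 0.2, c = 0.5):

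| Two-lesion patients | Lesions | Overall accuracy | 95% half-width |
|---|---|---|---|
| 10 | 50 | (24.3 + 14.4)/50 = 77.4% | 11.6 points |
| 20 | 60 | (16.2 + 28.8)/60 = 75.0% | 11.0 points |
| 30 | 70 | (8.1 + 43.2)/70 = 73.3% | 10.4 points |

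The movement from top to bottom is 77.4 − 73.3 = 4.1 points.

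**Distance from an all-one-injection figure.** For f of 5%, 10% and 20%, c from f to 1, and 10 or 20 two-lesion patients, the distance runs from 0 to 8.6 points. The largest value, at f = c = 0.2 and k = 10, is 80.6% against 72.0%, where the half-width is 11.0 points. In each of these scenarios the distance is smaller than the half-width.

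**Dependence on the scoring rule.** The protocol keeps inadequate lesions and offers an indeterminate label, but does not say how that label enters sensitivity, specificity or accuracy. Suppose indeterminate lesions are reported separately, and accuracy is computed on the rest. With n single lesions, accuracy is 0.9 × n(1 − f × c) / [n(1 − f × c)] = 90%. For two-lesion patients it is 0.9 × n(1 − f) / [n(1 − f)] = 90%. The gap is zero for every f and for every c. Only the indeterminate rate differs: f × c against f, or 10% against 20% at f = 0.2 and c = 0.5.

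**The case for a change.** The strongest argument for the concern is about data capture. A statistical analysis plan can split results by number of lesions or injections, but it cannot recover a first-injection diagnosis that nobody recorded. Once the same readers have seen the second-injection images, an unbiased first-injection read by them is gone. A split is also an imperfect substitute, because single and paired lesions may differ in size and disease pattern as well as in injections. And sampling error does not excuse a systematic shift in what an estimate means.

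Part of this stands. The mixing follows from the text, whether accuracy is counted per lesion or per patient, and a small shift relative to the half-width would not settle the matter alone. But the loss matters only if accuracy after one injection is the quantity wanted, and the protocol does not set that as its target. Basing the main figure on first-injection reads would set aside images obtained under the protocol, and statisticians could reasonably disagree about doing so.

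Nor would it give a uniform basis. In a two-lesion patient, one lesion's only injection is the patient's second, and differences in size and case mix remain. The constant 72.0% that such a read shows in the illustration results from assuming equal performance in all lesions.

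The remaining claims rest on silence. The protocol does not describe the read form, the viewing order or how images are stored by injection, and nothing says that injection counts go unrecorded. Showing results by number of lesions or injections is a reporting detail commonly left to the analysis plan, which is not at hand.

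**Conclusion.** The concern does not hold. The injection rule is explicit and consistent, and following it gives a sound descriptive accuracy for CEUS as performed under that rule. Preferring a one-injection test is a choice of estimand, not the correction of an error.

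The possible size is unknown from the protocol. With f up to 20% the assumed gap between single and paired lesions runs from 0 to 14.4 points; the central example moves overall accuracy by 4.1 points across a wide range of case mix. These figures need assumed failure and repeat rates, 90% accuracy on adequate images, and inadequate images counted as not correct. Without that last assumption the accuracy gap disappears. How indeterminate reads are counted is a separate question and does not turn on the injection rule. For a descriptive pilot of 40 patients with no power claim, nothing in the Methods text needs to change on this account.

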## Aim

In patients with hepatic lesions, to evaluate the efficacy of contrast enhanced ultrasound (CEUS) compared to MRI in differentiating focal nodular hyperplasia (FNH) and hepatic adenoma. Studies from Europe (Dietrich et al, Roche et al) have described different patterns of enhancement between FNH and hepatic adenoma. MRI is the current imaging modality of choice for making this determination, but has limitations. This pilot study aims to test the hypothesis that CEUS has similar ability to differentiate FNH and adenoma, using MRI as the gold standard.

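### Does a three-way CEUS read make the planned sensitivity, specificity and accuracy unusable without a written scoring rule?

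*Protocol*

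**What the plan says.** All the relevant text is in the protocol's Methods section, apart from the hypothesis in Aim.

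- **Read scale.** "Each lesion assessed will be given a presumed diagnosis of FNH, HA, or indeterminate".
- **Retention.** The rule for a lesion that is poorly seen is this: "if the injection(s) do not provide adequate images, the lesion in question will not be excluded from the study". The reason given for it is an intention-to-treat one: "Since the intention to treat includes all lesions chosen from MRI".
- **Purpose of the comparison.** The CEUS reads are set against the official MRI reports "to assess concurrence between the two imaging modalities".
- **Statistics.** "We will compile descriptive statistics comparing the sensitivity, specificity, and accuracy of CEUS for differentiating FNH and hepatic adenoma". MRI serves as the reference standard for all three measures.
- **Timing.** The reads take place "Once the study is closed to enrollment and all subjects have completed the research CEUS scan", in consensus by two radiologists who do not see the MRI findings.
- **Hypothesis (Aim).** "CEUS has similar ability to differentiate FNH and adenoma, using MRI as the gold standard".

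The protocol does not say whether FNH or HA is the positive class. Nor does it say how an indeterminate read, or a retained lesion with poor images, enters a numerator or denominator.

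**The concern.** Sensitivity and specificity need a two-way test result and a named positive class. The protocol supplies a three-way result and names no positive class. Several scorings are in common use, and they treat an indeterminate read in opposite ways. If it counts as test-negative, it is a miss in the positive class but a success in the other, although it has not told the two lesions apart. If it is dropped, it disappears from the figures, which sits badly with the retention sentence.

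These three measures are the only statistics named for the hypothesis in Aim. If the scoring were chosen after the results were seen, the more flattering version could be reported, and results could not be compared with other studies unless the rule was stated.

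**Working it through.** **Inputs from the protocol.** There are three read categories, 40 patients (Enrollment) and up to two lesions each (Methods), so 40 to 80 lesions if all are enrolled and scanned. The protocol gives no indeterminate rate, lesion mix, accuracy, power or threshold, so it has no figure to reproduce.

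**Assumptions made here.** All lesions are FNH or HA on MRI. The share correct among determinate reads is a = 0.90 and the indeterminate rate is r, both the same in the two classes. The mix is 30 FNH:10 HA or 20:20.

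**Formulas.** Let q be the share of lesions in the negative class.

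- Indeterminate counted as not correct: sensitivity = specificity = accuracy = a(1−r).
- Indeterminate counted as test-negative: sensitivity = a(1−r); specificity = a(1−r) + r; accuracy = a(1−r) + qr.
- Indeterminate counted as test-positive: sensitivity = a(1−r) + r; specificity = a(1−r); accuracy = a(1−r) + (1−q)r.
- Indeterminate dropped: all three = a.

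**At r = 0.20.** The value of a(1−r) is 0.90 × 0.80 = 0.72.

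- Not correct: accuracy 72%.
- Test-negative, FNH positive, 30:10: (30 × 0.72 + 10 × 0.92)/40 = 30.8/40 = 77%.
- Test-negative, HA positive, 30:10: (10 × 0.72 + 30 × 0.92)/40 = 34.8/40 = 87%.
- Test-negative, either class positive, 20:20: (0.72 + 0.92)/2 = 82%.
- Dropped: 90%.

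Test-positive scoring gives the same accuracies with the classes exchanged. Sensitivity and specificity are each either 72% or 92% when lesions are kept.

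**Spread in accuracy over the rules.** With all lesions kept it is 0.75r at 30:10 and 0.5r at 20:20, whatever the value of a. If dropping is also allowed, it is a − a(1−r) = ar for either mix.

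| Indeterminate rate | Accuracy, counted as not correct | Spread, kept, 30:10 | Spread, kept, 20:20 | Spread if dropping is allowed |
|---|---|---|---|---|
| 0% | 90% | 0 | 0 | 0 |
| 5% | 85.5% | 3.75 points | 2.5 points | 4.5 points |
| 10% | 81% | 7.5 points | 5 points | 9 points |
| 20% | 72% | 15 points | 10 points | 18 points |
| 30% | 63% | 22.5 points | 15 points | 27 points |

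**Check with whole lesions.** Take 30 MRI-FNH lesions with 6 indeterminate and 2 wrong, and 10 MRI-HA lesions with 2 indeterminate and 1 wrong. Correct reads are 22 + 7 = 29.

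- Not correct: 29/40 = 72.5%.
- Test-negative, FNH positive: (29 + 2)/40 = 77.5%.
- Test-negative, HA positive: (29 + 6)/40 = 87.5%.
- Dropped: 29/32 = 90.6%.

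**What the text already settles.**

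1. Accuracy, taken as the share of lesions on which CEUS and MRI give the same diagnosis, needs no positive class. It comes to depend on one only if indeterminate reads are forced into test-negative or test-positive.
2. On its plain meaning, an indeterminate CEUS does not concur with an MRI report of FNH or HA. The stated purpose therefore favours counting it as not correct.
3. The retention sentence speaks against dropping lesions with poor images, so the last column of the table relies on a rule that the document disfavours.
4. Neither statement settles specificity or names the positive class.

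**The case for a change.** The case for changing the text is that the protocol itself chose the read scale, the retention rule and the summary measures, and these do not fit together without a further rule. On this view it is more than detail deferred to another document. The retention sentence covers poor images and does not expressly cover a lesion that was imaged well and still read as indeterminate, so dropping those is not ruled out. Even with every lesion kept, the whole-lesion example leaves accuracy anywhere from 72.5% to 87.5%, and FNH sensitivity from 22/30 = 73.3% to 28/30 = 93.3%. The remedy would be short, would need no new data, and could be in place before any read.

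Much of this stands. The rule is unwritten, the arithmetic is right, and a sentence on scoring would help whoever runs the analysis. But the three stated elements are compatible under several ordinary rules, and none of them produces a wrong result as written. What is absent is a scoring convention, the kind of detail that a protocol commonly leaves to the statistical analysis plan. The readers do not see the MRI findings, so the scoring cannot alter the reads. Fixing it in advance guards against selective choice, but the figures can still be interpreted if the report states the rule or shows the table of three CEUS results by two MRI diagnoses.

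**Conclusion.** No change to the plan follows. The protocol leaves open how an indeterminate or poorly imaged lesion enters sensitivity and specificity, and which lesion is the positive class. This is missing detail that analysts can fill sensibly, and not an error in a stated rule. The document's own statements point to keeping these lesions and counting them as not correct for accuracy.

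The possible size is about 10 points of accuracy at a 20:20 mix and 15 points at 30:10, if 20% of reads are indeterminate and all lesions are kept. It shrinks in proportion to the indeterminate rate and is nil when there are no such reads. Every one of these percentages rests on assumed rates and shows what could happen, not what is expected. The study is a pilot with descriptive statistics, no threshold and no power claim, so no formal decision turns on the choice.

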## **Enrollment**

As this study explores a new method of diagnosing hepatic lesions and there is little published data on the subject, we do not have sufficient knowledge to do power and sample size calculations to demonstrate the number of patients needed to show equivalence between the two imaging methods. The proposed enrollment of 40 patients reflects the availability of both Lumason and the approximate number of qualifying patients who would undergo MRI for evaluation of these lesions in one year.

## **Resources/Budget**

At the performance site, patients with suspected FNH or HA typically undergo MRI of the liver as part of standard of care, and the patient or insurer will be billed for the examination and radiologic interpretation. CEUS is not routinely performed in this population. The cost

associated with CEUS and the time of the investigators will be the responsibility of the Department of Radiology and Imaging Sciences.

Subjects will be compensated for their time and effort with a \$50.00 gift card upon completion of research imaging.

